1 BACKGROUND AND RATIONALE

1.1 Background

1.1.1 Acute myeloid leukemia

Acute myeloid leukemia (AML) is a malignancy of hematopoietic progenitor cells ⁽²⁾. Patients below an age of 60 years are treated with 1-2 cycles of standard chemotherapy usually with cytosine arabinoside (Ara-C) and daunorubicin according to the 7 + 3 schedule. Between 70-80% of patients achieve a complete remission. Both American ^(3, 4) and European ⁽⁵⁾ cooperative group studies have found that the choice of anthracycline (daunorubicin or idarubicin, or the anthracenedione mitoxantrone) is of little consequence, assuming equitoxic doses are administered. Thereafter, patients receive consolidation therapy which is guided by the European LeukemiaNet (ELN) risk criteria ^(6, 7). Patients with good risk receive several cycles high dose Ara-C^(8, 9), patients with intermediary risk I and II and patients with unfavorable prognosis are transplanted in first CR if a suitable donor is available and no contraindications to stem cell transplant exist. In Germany, up to two thirds of patients receive an allotransplant in first remission. With this strategy 70-80% of patients are cured in the good risk category ^(10, 11), 50% in the intermediary risk and 20-40% in the high risk category ⁽¹²⁾.

Recurrent/ Relapsed AML

Patients with relapsed AML usually have a dismal prognosis⁽¹³⁾. The best outcome is achieved in patients who receive an allotransplanting with about 20% - 40% of patients being long term survivors ⁽¹⁴⁾. The best results with allografting are achieved in patients who have achieved a second remission ⁽¹⁵⁾. The chance of a second CR depends of the duration of the first remission, the karyotype and the performance status of the patient.

No standard regimen exists for the treatment of patients with relapsed acute myeloid leukemia (AML), particularly in patients with a first remission duration of less than 1 year ⁽¹⁶⁾. A number of agents have activity in recurrent/relapsed with an overall response rate of 20-80%, depending on study design and treatment (see Table 1, Appendix 1). Re-induction with Ara-C and daunorubicin will result in a 50% CR rate in patients who had a first remission lasting longer than 1 year ⁽¹⁷⁻¹⁹⁾. In a trial of mitoxantrone in combination with Ara-C in patients with refractory or relapsed AML with 49 patients 62.5% with first relapse AML achieved complete remission while none of the four patients with more than one prior remission responded ⁽²⁰⁾. A triple combination of mitoxantrone, etoposide, and cytarabine (MEC) demonstrated a CR induction rate of 55% in a population including 30 patients with relapsed AML, 28 patients with primary refractory AML, and 16 patients with secondary AML ⁽²¹⁾. A phase 1-2 study of clofarabine plus Ara-C in 25 patients with relapsed acute myeloid leukemia 7 (22%) achieved complete remission (CR), and 5 (16%) achieved CR with incomplete platelet recovery (CRI), for an overall response rate of 38% ⁽²²⁾. For patients not achieving a complete remission the only potentially curative treatment option is allogeneic transplantation with up to 20% of patients being long term survivors ⁽¹⁴⁾.

Therefore, the combination of Ara-C and idarubicin was chosen for standard induction therapy and if the patient receives complete remission transplantation is recommended.

In the light of a dismal prognosis for patients with relapsed/refractory AML a great clinical need exists for new treatment options.

1.1.2 Selinexor

Over 10 major tumor suppressor pathways have evolved in order to prevent the development and progression of neoplasia. Because the vast majority of tumor suppressor (TSP) and growth regulatory (GRP) proteins require nuclear localization in order to carry out their antineoplastic activities, enhancing their nuclear export leads to their functional inactivation. The major TSP/GRP are exported exclusively by the protein CRM1 (also called XPO1), and tumors showing elevated CRM1 levels with cytoplasmic mislocalization of TSP/GRP.

Additional detailed information is provided in the Investigator's Brochure.

Selinexor is an orally available, irreversible, potent and Selective Inhibitor of Nuclear Export (SINE) that specifically blocks XPO1. It is selectively cytotoxic for cells with genomic damage, i.e., for tumor cells, both *in vitro* and *in vivo*. Normal cells, with minimal or no DNA damage, remain in transient, reversible cell cycle arrest until the export block is relieved. Selinexor and other SINE compounds are not intrinsically cytotoxic; rather, they can restore the highly effective tumor suppressing pathways that lead to selective elimination of genetically damaged (i.e., neoplastic) cells. Tumors of hematopoietic lineage are particularly susceptible to induction of apoptosis by XPO1 inhibition; normal hematopoietic cells and their functions are largely spared.

1.1.2.1 Preclinical Efficacy

In vitro experiments with continuous (~72 hour) exposure to Selinexor demonstrated potent pro-apoptotic activity across a broad panel of tumor-derived cell lines and patient samples in culture including multiply-resistant cancers, with the majority of IC50s for cytotoxicity <800 nM and most hematologic tumor lines having IC50s of 20-400 nM for Selinexor. In contrast, normal cells typically underwent (or remained in) cell cycle arrest but were resistant to apoptosis-induction; cytotoxicity IC50s were typically >5 µM. Efficacy was demonstrated in mouse models of myeloma, mantle cell lymphoma (MCL), and T-cell acute lymphocytic leukemia (T-ALL) xenografts. Moreover, efficacy including significant survival advantages was demonstrated in acute myeloid leukemia (AML) [MV4-11 (FLT3-ITD)]^(23, 24) and chronic lymphocytic leukemia (CLL) (TCL-1) leukemographs. Efficacy was also demonstrated in solid tumor xenografts including prostate, breast, liver, glioblastoma, kidney and colon cancers. KPT-276 and KPT-335, SINEs closely related to Selinexor, have been given orally to several dogs with various cancers in ongoing pilot studies, and clear evidence of antitumor activity with acceptable tolerability has been obtained in dogs with both *de novo* newly diagnosed and chemotherapy (e.g. CHOP- (cyclophosphamide, hydroxydaunorubicin, oncovin and prednisone-resistant diffuse large B cell non-Hodgkin's lymphoma (DLBCL) in dogs. In a Phase 2b study of newly diagnosed or first relapsed NHL (mainly DLBCL) in dogs, KPT-335 induced a 34% objective response rate (≥50% tumor shrinkage) as a single agent. Reduced food intake, which can be accompanied by weight loss, was observed; food supplementation can largely overcome this and dosing has been maintained for over 6 months in dogs with cancer.

1.1.2.1.1 Preclinical Efficacy: AML

AML cells overexpress the nuclear exporter, Exportin 1 (XPO1/CRM1) and higher XPO1 levels correlate with poor outcome⁽²⁸⁾. The novel selective inhibitor of nuclear transport (SINE), Selinexor, antagonizes XPO1 and shows potent cytotoxicity for AML and ALL cells *in vitro*, independent of genotype.

Selinexor show potent antiproliferative effect and induced apoptosis, cell cycle arrest and myeloid differentiation in AML cell lines and patient blasts, including those from patients with NPM1 and FLT3-ITD mutations⁽²³⁾.

Mechanistic studies show that SINE induces nuclear localization and activation of multiple tumor suppressor proteins (TSPs), leading to rapid apoptosis of AML cells. In addition, a strong down-regulation of the oncogenes FLT3 and c-KIT were observed after SINE treatment in both FLT3-ITD and wild-type cell lines⁽²³⁾. Selinexor treatment also restored the localization of cytoplasmic mutant NPM1 into the nucleus.

In murine AML and ALL models, Selinexor showed potent antileukemic activity without toxicity to normal hematopoietic cells^(23,24,29).

1.1.2.2 Preclinical Safety

In the Selenixor nonclinical safety program in Sprague-Dawley rats and cynomolgus monkeys, the primary effects of oral Selinexor were dose-dependent reductions in food intake and body weight (or reductions in body weight gain), with minimal clinical symptoms (no or mild non-bloody diarrhea), associated primarily with gastrointestinal atrophy. Similar effects are observed in mice and dogs. At high repeated doses of Selinexor associated with marked weight loss, there were changes in cerebellar granular layer neurons in both rats (≥ 300 mg/m²) and monkeys (≥ 72 mg/m²), but only monkeys showed any CNS symptoms. No central nervous system (CNS)-related adverse side effects were observed in the GLP, rat and monkey 4-cycle toxicity studies. A GLP, rat neurofunctional study (Irwin test) has also been performed at dose levels of 12, 60, or 300 mg/m² (2, 10, and 50 mg/kg). No behavioral changes were observed at all doses tested.

In the pivotal, GLP, 4-week monkey study, there was no evidence of a direct or indirect effect of Selinexor on the morphology and intervals of the ECG at up to 36 mg/m² (3 mg/kg). Based on these results, QT prolongation or other cardiac effect does not appear to be a safety concern for Selinexor.

In summary, dose limiting toxicity (DLT)/mortality in both rats and monkeys is related primarily to marked weight loss with atrophy of the gastrointestinal (GI) tract and noncritical effects on other major organs.

Further detailed information is provided in the Investigator's Brochure.

1.1.2.3 Clinical Efficacy

Karyopharm Therapeutics is currently conducting three open label Phase 1 clinical trials to assess the safety, tolerability and efficacy of Selinexor given orally 2-3 times per week. The first study (KCP-330-001) is a dose escalation study in patients with advanced hematological malignancies, the second (KCP-330-002) is a dose escalating study in patients with advanced or metastatic solid tumor malignancies and the third (KCP-330-003), a food effect study, is in patients who have metastatic, locally advanced or locally recurrent soft tissue or bone sarcomas. All patients entering these single-agent phase 1 studies have relapsed after available therapies and have objectively progressing tumors at time of study drug initiation. To date Selinexor has been administered to over 130 patients. The food effect study was initiated in July 2013, so preliminary safety or efficacy data are not yet available.

In the Phase 1 study (KCP-330-001) a total of 39 patients with relapsed AML have been enrolled. As of December 4, of 33 pts who were evaluable for response, complete response (CR) with full hematological recovery was achieved in 4 patients (11%), and CR without hematological recovery (CRi) in 1 patient (3%). Partial Response (PR) was achieved in 2 patients (6%). Morphological leukemia free state was achieved in 1 patient (3%). Ten (29%) of the remaining patients have had stable disease for > 30 days, and 13 (34%) have had progressive disease.

Table 1: Responses in Arm 2 (AML) [16.8 mg/m² to 40 mg/m²] (Study KCP-330-001) as of December 4, 2013

Responses in Arm 2 Acute Myeloid Leukemia Patients as 4-Dec-2013								
Number of Pts Evaluated	Total CRs, CR(i)s, PRs, and SD (%)	CR (%)	CR (i) (%)	PR (%)	MLFS (%)	SD (%)	PD	WC
33	18 (55%)	4 (12%)	1 (3%)	2 (6%)	1 (3%)	10 (30%)	11 (33%)	4 (12%)

Abbreviations: N=number of patients, CR=complete remission, CRi=complete remission without platelet recovery, PR=partial response, MLFS=morphological leukemia free state, SD=stable disease, PD=progressive disease, NE=not evaluable, WC=withdrew consent.

1.2 Study Rationale

Selective inhibition of nuclear export (SINE) is a novel therapeutic strategy that could potentially be applicable to many cancers. Tumors of hematopoietic lineage are particularly susceptible to induction of apoptosis by XPO1 inhibition; normal hematopoietic cells and their functions are largely spared. *In vivo* efficacy was observed with Selinexor treatment groups in mouse models of different types of cancer. Moreover, efficacy including significant survival advantages was demonstrated in acute myeloid leukemia (AML) [MV4-11 (FLT3-ITD)]^(23, 24), and chronic lymphocytic leukemia (CLL) (TCL-1) leukemografts. These studies demonstrate potent *in vitro* and *in vivo* efficacy of Selinexor against a variety of cancer tumor models as a standalone agent or in combination with a variety of anti-cancer modalities.

In a recent study the safety and efficacy of Selinexor and Ara-C as single agent or in combination was tested *in vivo*. Treatment with AraC or Selinexor alone significantly prolonged the survival of leukemic mice from a median survival of 24 days (APL + vehicle) to 33 days or 39 days, respectively ($P < 0.0001$). Encouragingly, combination therapy with AraC + KPT-330 further prolonged survival compared to monotherapy ($P < 0.0001$), with some mice being cured of the disease.

In the Phase 1 study (KTP-330-001) 5 out of the 33 AML patients (15%) have experienced a complete remission (CR)/ complete remission without platelet recovery (CRI).

Because of the encouraging efficacy, unique mechanism of action and clinical safety, it is considered to be a suitable agent to study in the combination with Ara-C and Idarubicin.

2 OBJECTIVES OF THE STUDY

2.1 Primary Objective

The primary objective is to determine the efficacy of Selinexor in patients with relapsed/ refractory AML by complete response rate (CR) or CRi, as defined by the recommendations on diagnosis and management of AML in adults from an international expert panel, on behalf of the European LeukemiaNet⁽¹⁾.

2.2 Secondary Objectives

Secondary objectives of the study are:

- To determine the efficacy of Selinexor in combination with standard chemotherapy in patients with relapsed/ refractory AML by:
 - Rate of partial remissions
 - Percentage of patients being transplanted after induction therapy
 - Early death rate
 - Overall survival (OS)
 - Event-free survival (Events are defined as Death, not achieving a CR or CRi, Relapse after CR or CRi)
- To evaluate overall safety and tolerability of Selinexor characterized by type, frequency, severity (graded using the National Cancer Institute Common Terminology Criteria for Adverse Events [NCI CTCAE] Version 4.03), timing and relatedness of adverse events (AEs) and laboratory abnormalities observed during the treatment within this study

2.3 Exploratory Objectives (Optional Studies)

- Translational Research on Patient Leukemic Blast Cells
 - Selinexor-induced changes in gene expression profile of leukemic blasts isolated from patients
 - Expansion of leukemic blasts in mice for therapeutic studies
- Pharmacokinetics and Pharmacodynamics of Selinexor in patients with relapsed/refractory AML will be assessed in an explorative manner.
 - Limited PK to assess Selinexor plasma level
 - Pharmacodynamic assessments
 - Selinexor-induced changes in mRNA levels of XPO1 and tumor suppressor markers from leukocytes
 - Selinexor-induced changes in plasma cytokine levels

3 STUDY DESIGN

3.1 Overview of Study Design and Dosing Regimen

This is a multi center, open-label, non-randomized phase II trial study.

Patients are informed, screened and enrolled in the study at the time of progression of disease on prior chemotherapy documented by Bone Marrow Aspirate. Treatment should start within two weeks after enrolment.

The study design is displayed in Figure 1.

3.1.1 Baseline Translational Research Study (optional)

All enrolled patients may participate in an optional baseline translational research study. Patients will receive single dose of Selinexor (60 mg) after registration and before first induction cycle. Bone marrow aspirate samples will be collected pre-dose and 24 hour post-dose. Blast cells will be used for leukemic stem cell gene expression profiling and in mouse model studies to define parameters associated with clinical responsiveness to Selinexor. See 5.1.2.1 for more details.

3.1.2 Definition of Treatment Cycle

All enrolled patients will be treated with cytosine arabinoside (Ara-C) at a dose of 100 mg/m² continuous infusion (day 1-7) and idarubicin at a dose of 10 mg/m² i.v. (days 1,3,5) every 4 weeks and Selinexor for a maximum of 2 cycles. During the second cycle the idarubicin dose is restricted to 2 administrations on day 1 and 3.

[figure not shown]
Patients will receive oral Selinexor 60 mg twice weekly in weeks 1-3 of a 4-week cycle (Monday/ Wednesday or Tuesday/ Thursday or Wednesday/Friday) starting on day 2 of week 1 (total of 6 doses per induction cycle).

If a CR or CRi was achieved, patients will be recommended for stem cell transplantation. If a PR is achieved patients can undergo a second, identical treatment cycle.

In patients who are not eligible or do not undergo additional stem cell transplantation, but, in the opinion of the investigator, are benefiting from Selinexor, then oral Selinexor dosed twice weekly in weeks 1-3 of a 4-week cycle may be continued parallel to 3 cycles of consolidation therapy with Ara-C until relapse or toxicity develops. The dose of Ara-C is 3 g/m² IV for 2h every 12 hours at 3 consecutive days for patients with good performance status and younger than 60 years (in total 6 doses). If patients are older than 60 years the dose is 1 g/m² IV for 2h every 12 hours at 3 consecutive days. During consolidation Selinexor dosing (60 mg) will start on day 2 of week 1 of a 4-week cycle and will be continued twice weekly during weeks 1-3 of a 4-week cycle (total of 6 doses per cycle). Selinexor twice weekly (Monday/ Wednesday or Tuesday/ Thursday or Wednesday/Friday) in weeks 1-3 at a dose of 60 mg (total of 6 doses per 4-week cycle) may continue until relapse or for maximally 1 year of treatment.

Patients achieving a > 50% blast reduction after the end of 2 induction cycles and in the opinion of the investigator, are benefiting from Selinexor and are not candidates for Stem cell transplantation, oral Selinexor dosed twice weekly in weeks 1-3 may be continued. Drug administration will occur twice weekly, on days 1 and 3 of weeks 1-3 of a 4-week cycle at a dose of 60 mg (e.g. on Monday and Wednesday or on Tuesday and Thursday or on Wednesday and Friday). One cycle is 4 weeks with 6 doses of Selinexor.

Safety assessments are performed at baseline visit, twice weekly during induction treatment, at the End of Cycle and at the End of Treatment visit. Clinical and Bone Marrow Aspirate for disease status are performed at baseline, at the end of the cycle during induction and consolidation. During maintenance and follow-up after SCT bone marrow aspirate is required in case of suspicious blood counts. If a patient discontinues treatment due to any other reason than disease progression/ death/ withdrawal of informed consent, the disease evaluations shall continue until disease progression. This includes patients who wish to discontinue treatment, but agree that further data is captured for the purpose of the study (partial withdrawal).

Figure 1: Study Flow Chart

3.1.3 Treatment Duration

Treatment duration for patients achieving CR or CRI during induction will be 1 or 2 cycles of 4 weeks each. These patients will be recommended for stem cell transplantation and have their end of treatment prior to SCT and will be followed for event-free and overall survival.

For patients achieving CR or CRI but who are not eligible or do not undergo additional stem cell transplantation, will continue in consolidation/maintenance therapy with 3 cycle of AraC combined with 4-week cycles with twice-weekly Selinexor during weeks 1 and 3 until relapse (for maximally 1 year of treatment).

Patients with a > 50% blast reduction at the end of 2 induction cycles and in the opinion of the investigator, are benefiting from Selinexor, will in maintenance therapy with 4-week cycles with twice-weekly Selinexor in weeks 1-3 until progression of disease (for maximally 1 year of treatment).

For patients for whom none of the above mentioned is achieved after 2 4-week induction cycles will discontinue study and will be followed for overall survival.

In any case, treatment will be discontinued upon progression of disease (PD) or unacceptable toxicity, withdrawal of consent by the patients, or non-compliance by the patient with protocol requirements.

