Treatment scheme	
All enrolled patients may participate in an optional baseline translational research study. Patients will receive single dose of Selinexor (60 mg) after registration and before first induction cycle. Bone marrow aspirate samples will be collected pre-dose and 24 hour post-dose.
 
All enrolled patients will be treated with Ara-C at a dose of 100 mg/m² continuous infusion (day 1-7) and idarubicin at a dose of 10 mg/m² iv (day 1,3,5) every 4 weeks and Selinexor. If a second cycles is applied idarubicin is only given on day 1 and 3).
 
Selinexor will be administered at a dose of 60 mg twice weekly orally during weeks 1-3 of a 4-week cycle (day 2,4,9,11,16,18) (total of 6 doses per induction cycle).
 
If a CR was achieved the patient will be recommended for stem cell transplantation and will have his/her end of treatment and will be followed for event-free and overall survival.
 
If patient has achieved a PR an additional cycle (4 weeks) will be initiated. If a CR was achieved the patient will be recommended for stem cell transplantation and will be followed for event-free and overall survival.
 
In patients achieving CR or CRi after 1 or 2 4-week cycles who are not eligible or do not undergo additional stem cell transplantation, but, in the opinion of the investigator, are benefiting from Selinexor, then oral Selinexor dosed twice weekly may be continued parallel to consolidation therapy with Ara-C until relapse or toxicity develops. The dose of Ara-C is 3 g/m² IV for 2h every 12 hours at 3 consecutive days for patients with good performance status and younger than 60 years (in total 6 doses). If patients are older than 60 years the dose is 1 g/m² IV for 2h every 12 hours at 3 consecutive days. Consolidation with AraC will consist of 3 4-week cycles. During consolidation Selinexor dosing (60 mg) will start on day 2 and continue twice weekly in weeks 1-3 of a 4-week cycle (total of 6 doses per cycle). Selinexor twice weekly (with ~48 hours between two consecutive doses) in weeks 1-3 of a 4-week cycle at a dose of 60 mg (total of 6 doses per 4-week cycle) may continue until relapse or for maximally 1 year of treatment.
 
Patients achieving a > 50% blast reduction after the end of 2 induction cycles, not candidates for SCT, and in the opinion of the investigator, are benefiting from Selinexor, oral Selinexor dosed twice weekly may be continued until PD or for maximally 1 year of treatment. Drug administration will occur twice weekly with ~48 hours between two consecutive doses at a dose of 60 mg. One cycle is 4 weeks with 6 doses of Selinexor during weeks 1-3. (e.g.

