6.2.2 Route of Administration

Selinexor tablets will be taken orally twice weekly during weeks 1-3 of a 4-week cycle, either on Monday and Wednesday or on Tuesday and Thursday or on Wednesday and Friday.

Selinexor is to be taken within approximately 30-minutes of solid food consumption together with 240 mL (8 ounces) of water.

Each dose will consist of Selinexor for oral administration with a dose of 60 mg.

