6.3 Dose modification of Selinexor

Toxicity will be graded according to NCI CTCAE, version 4.03; the therapy modifications described below are applied according to this severity grading.

Each dose modification or treatment delay has to be documented in the CRF, including the respective reason.

Based on observations from the ongoing Phase 1 studies in patients with advanced hematological and solid tumors, Selinexor (KPT-330) shows a wide therapeutic range, with documented anti-leukemic activity from $\sim 17\text{mg}/\text{m}^2$ to $\geq 55\text{mg}/\text{m}^2$ orally twice weekly. At the present time, we cannot predict which patient's leukemia will respond to lower doses, nor can tolerability be predicted. Therefore, in order to individualize and optimize therapeutic benefit with this oral SINE XPO1 antagonist, initiation of study therapy will be with a relatively high dose (60 mg twice weekly in weeks 1-3 of a 4-week cycle by mouth) of Selinexor. Although this is a high dose, it is below the MTD of oral Selinexor, and we believe will maximize early disease control with good tolerability in the majority of patients. Flexible dose reductions and/or schedule modifications will be permitted. In patients with tolerability issues on Selinexor, it is recommended either: (1) reducing Selinexor dose by 30% or (2) reducing Selinexor dosing frequency to once weekly.

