6.3.1 Dose Adjustment Guidelines for Selinexor Related Toxicities

Toxicity will be graded according to NCI CTCAE, version 4.03; the therapy modifications described below are applied according to this severity grading.

If more than one different type of toxicity occurs concurrently, the most severe grade will determine the modification.

Re-escalation of the study drug is allowed as outlined in the sections that apply for the specific toxicity. If drug-related toxicity requires a treatment delay of more than 28 days the patient is taken off protocol treatment.

Each dose modification or treatment delay has to be documented, including the respective reason.

Table 2: Prespecified dose/schedule modifications for adverse events related to study drug

Dose level	Dose of Selinexor
Dose level 0	60 mg twice weekly (D1, D3)
Dose level -1	50 mg twice weekly (D1, D3)
Dose level -2	40 mg once weekly (D1)
Dose level -3	30 mg once weekly (D1)
Dose level -4	Discontinue dosing

Based on observations from the ongoing Phase 1 studies in patients with advanced hematological and solid tumors, we note that selinexor shows a reasonably wide therapeutic range, with activities from $\sim 10\text{mg}/\text{m}^2$ to $\geq 50\text{mg}/\text{m}^2$. Therefore, in order to optimize specific anti-tumor activity and the patient's tolerability, we will allow for dose and/or schedule modifications as described below. Patients should also be treated aggressively with supportive care to reduce toxicities.

Table 3: Criteria for dose adjustments of Selinexor-related toxicities

Toxicity and Intensity	Dose Modification
Fatigue (common)	
Grade 1	Insure adequate caloric intake and assess volume status. Adjust other medications. Consider addition of low dose corticosteroids (e.g., 4 mg dexamethasone with each dose of Selinexor or 10 mg prednisone per day every day). Rule out other causes of fatigue such as adrenal insufficiency.
Grade 2	Insure adequate caloric and fluid intake and assess volume status. Add corticosteroids on day of Selinexor (e.g., 4 mg dexamethasone), or give or 10-15mg prednisone every other day. If fatigue dose not resolve to Grade 1, increase corticosteroids to the day of and the day after Selinexor dosing, and/or reduce dose of Selinexor by one level (Table 2).

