
All dose modifications should be based on the worst preceding toxicity.
 
Isolated values of ≥ Grade 3 alkaline phosphatase values will NOT require dose interruption.
 
Determination of liver vs. bone etiology should be made, and evaluation of gamma-glutamyl transferase (GGT), 5'-nucleotidase (5'NT), or other liver enzymes should be performed.
 
Patients are allowed dose reductions to a minimum dose of 15 mg/m² as described in Table 2.
 
If a patient requires a dose interruption of > 28 days, then the patient must be discontinued from the study. Patients who discontinue the study for a study related adverse event or an abnormal laboratory value must be followed at least once a week for 28 days and subsequently at 28 day intervals until resolution or stabilization of the event, whichever comes first.
 
a. Common Terminology Criteria for Adverse Events (CTCAE Version 4.03) otherwise specified values.
	

For all ≥ Grade 3 hematological or non-hematological AEs that are NOT Selinexor related:

After consultation with the Medical Monitor and at the discretion of the treating physician, Selinexor dosing may be maintained provided that the patient can continue to take the agent by mouth, or via other enteral route.

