The sample size calculation ended up in 25 patients to be recruited to ensure a power of 90 % for the discrimination of p_0 and p_1 . In addition, 15 additional patients were submitted to an adapted drug regimen (flat dose 60mg of Selinexor instead of 40 mg /m² of Selinexor). Using a similar approach, the power will be 80 % to discriminate a $p_0=30$ % from a $p_1=65$ %, with a one-tailed α of 0.05 %.

6 Statistical hypotheses

The purpose of this study is to evaluate efficacy of Selinexor in patients with relapsed/ refractory AML by complete response rate (CR or CRi). The null-hypothesis to be tested is

H_0 : *The observed response rate is less or equal than 30 %*

against the alternative hypothesis

H_1 : *The observed response rate is over 30 %*

7 Analysis sets

A detailed subject classification document will be prepared in a Data Review meeting prior database lock. The document will assign patients to the respective analysis sets depending on the observed protocol violations.

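### Two Selinexor dosing instructions contradict other protocol text: dosing weeks after CR/CRi without transplant, and a mg/m² minimum tied to a flat-dose table

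*Protocol*

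**What the plan says.** **Dosing weeks.** Protocol 3.1.3, on patients who reach CR or CRi but do not go on to transplant, combines three Ara-C cycles with "4-week cycles with twice-weekly Selinexor during weeks 1 and 3 until relapse", for at most one year. For the same patients, Protocol 3.1.2 says that Selinexor "in weeks 1-3 at a dose of 60 mg (total of 6 doses per 4-week cycle) may continue until relapse", again with a one-year maximum. The synopsis (Treatment scheme) says: "During consolidation Selinexor dosing (60 mg) will start on day 2 and continue twice weekly in weeks 1-3 of a 4-week cycle", and counts 6 doses per cycle. The general rule in 6.2.2 is that "Selinexor tablets will be taken orally twice weekly during weeks 1-3 of a 4-week cycle".

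**Minimum dose.** The notes to Table 3 in Protocol 6.3.1 state: "Patients are allowed dose reductions to a minimum dose of 15 mg/m² as described in Table 2". The dose-level table in that section lists 60 mg and 50 mg twice weekly, then 40 mg once weekly, then "30 mg once weekly (D1)", then discontinuation. It contains no per-area value. Section 6.3 also recommends, for patients who tolerate the drug poorly, either "1) reducing Selinexor dose by 30% or (2) reducing Selinexor dosing frequency to once weekly". Section 6.2.1.1 supplies 10 mg tablets only.

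**What the analysis plan does with dosing.** SAP 5 describes the 15 additional patients as receiving a "flat dose 60mg of Selinexor instead of 40 mg /m² of Selinexor". SAP 11 promises descriptive summaries of exposure and compliance, overall and by dosing schedule, without naming a planned number of doses. SAP 18 cites protocol Version 2 (25.08.2015); the protocol supplied is Version 3.1 (13.01.2017).

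**The concern.** Both items are operative instructions in current protocol text. Two doses a week in two weeks cannot make six doses, so the planned exposure of a non-transplanted CR/CRi patient depends on which section a site reads. The paragraph of 3.1.3 that follows gives patients with more than 50% blast reduction weeks 1-3, so a site could take the difference between the two groups as deliberate.

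The minimum dose has the same kind of problem. A patient can be reduced, exactly as the dose-level table allows, to a dose that the note citing that table does not allow.

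At stake are uniform treatment after induction and a clear reference for the exposure and compliance summaries.

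**Working it through.** **Step 1. Doses per cycle.** Doses per week × dosing weeks:

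| Source | Weeks | Doses per 4-week cycle | mg per cycle at flat 60 mg |
|---|---|---|---|
| Protocol 3.1.2, synopsis | 1-3 | 2 × 3 = 6 (reproduces the stated 6) | 6 × 60 = 360 |
| Protocol 3.1.3 | 1 and 3 | 2 × 2 = 4 | 4 × 60 = 240 |

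The second schedule has one third fewer doses (1 − 4/6).

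**Step 2. Over the pathway.**
- Three Ara-C cycles: 3 × 4 = 12 against 3 × 6 = 18 doses, or 720 against 1,080 mg.
- One-year maximum: 52/4 = 13 cycles if the year excludes induction, and 11 or 12 if it includes two or one induction cycles. That gives at most 44-52 against 66-78 doses (2,640-3,120 against 3,960-4,680 mg), and only for a patient who stays relapse-free and on treatment for the full year.

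**Step 3. How many patients.** The documents do not say. The mg figures apply to the flat dose, which SAP 5 assigns to 15 additional patients. At the 30% and 60% planning rates this is 0.30 × 15 = 4.5 to 0.60 × 15 = 9 responders, less those transplanted. The 65% and 70% alternatives set for these 15 patients would give 9.75 and 10.5.

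**Step 4. The minimum against the dose-level table.** Body surface area (BSA) is not reported, so 1.5 to 2.5 m² is assumed. The minimum in mg is 15 × BSA; the lowest level per area is 30/BSA.

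| BSA (m²) | Minimum (mg) | 30 mg expressed in mg/m² |
|---|---|---|
| 1.5 | 22.5 | 20.0 |
| 1.8 | 27.0 | 16.7 |
| 2.0 | 30.0 | 15.0 |
| 2.2 | 33.0 | 13.6 |
| 2.5 | 37.5 | 12.0 |

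The two agree only at 30/15 = 2.0 m²; above that, level -3 is under the stated minimum. Level -2 (40 mg) would be under it only above 40/15 = 2.67 m². Two tables in the protocol are numbered 2, but the one in 5.2 is the visit schedule, so the note can only mean the dose-level table in 6.3.1.

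**Step 5. The 30% reduction (minor).** 0.70 × 60 = 42 mg. This is no level in the table and cannot be made from 10 mg tablets, which give 40 mg (−33.3%) or 50 mg (−16.7%).

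**Step 6. Timing.** Assume last registration on 30 June 2016, start 14 days later, and one year of treatment with or without 56 days of induction on top. Dosing could then run to between 14 July and 8 September 2017. That is 182 to 238 days (6.5 to 8.5 cycles) after Version 3.1, and 208 to 264 days before the SAP addendum of 4 April 2018.

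**The case against.** The strongest case on the other side concerns weight. Section 3.1.3 stands alone against several passages and may be a slip. Version 3.1 postdates the end of enrolment, and the wording that governed earlier treatment is not in the documents. The minimum matters only at the lowest dosing level and only for larger patients, and the 30% reduction is a recommendation. Protocol 6.2 has all prescribed doses and dose changes entered in the CRF, and 6.2.3 adds doses given and missed doses with reasons, so given against prescribed can be computed per patient. By 2018 dosing had probably ended.

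Most of this stands, and it limits the size of the point. It does not remove the contradiction: the documents do not call 3.1.3 a slip, and the note on the minimum cannot be applied as its own reference directs.

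Four stronger readings are tempting but not supported:
- *That the liver rules in Table 3 also contradict each other.* One sentence uses total bilirubin with other causes ruled out; the other uses direct bilirubin without that condition. They sit in different toxicity rows, and both can hold as sufficient triggers. The AST/ALT Grade 2 row has its own delay instruction, and 6.3.1 lets the most severe grade decide when toxicities coincide.
- *That a large share of the 40 patients is affected.* Applying the planning rates to all 40 ignores that the mg figures concern the flat dose, and it does not subtract those transplanted.
- *That compliance would be misstated by a definite percentage.* The SAP gives no compliance formula, and its table plan lists exposure but no compliance table.
- *That the once-weekly option in 6.3 also conflicts with Table 3.* The bilirubin and diarrhea rows of Table 3 themselves use once-weekly dosing at an unchanged dose.

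**Conclusion.** The point holds for the dosing weeks and for the minimum dose. The first is a direct contradiction: 4 against 6 doses per cycle for the same patients. The second is a minimum in mg/m² that cites a flat-dose table and is undercut by that table's lowest level above 2.0 m². The 42 mg result is a minor companion.

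The per-cycle and three-cycle dose counts need no assumption; their mg equivalents take unreduced 60 mg doses. The one-year range depends on whether induction counts toward the year, and the BSA values are assumed. The origin of the mg/m² unit is not stated. It may be left over from the 40 mg/m² regimen, but that is conjecture.

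The planned induction schedule is stated consistently, and the SAP addendum rests the primary response on the best result after induction, so the primary analysis is not affected. The correction should be made because these are treatment instructions and it is cheap, not because the main result is at risk.

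**What to change.** The sponsor reconciles the passages by clarification or amendment. The dosing weeks for CR/CRi patients without transplant should be stated once and cross-referenced elsewhere. The minimum dose, the recommendation in 6.3 and the dose-level table should be made consistent with one another. Which schedule or minimum applies is for the sponsor to decide.

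SAP 11 should name, for each dosing schedule, the planned schedule and the protocol version that serve as the reference for the exposure and compliance summaries, using the prescribed doses recorded in the CRF. If dosing has ended, the sponsor documents which schedule sites were told to follow and uses it as that reference in the updated analysis and the study report.

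The cost is one clarification or amendment text, one sentence in SAP 11 and a note in the study report. No extra patients or procedures are needed. On the timing assumptions above, only the documentation and reference part was still open at the April 2018 addendum.
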